3.4.2 Secondary Study Endpoints

Phase R61:

- Aim 1: Target Engagement. Response to real-time vs sham neurofeedback will be determined by pre-post change in selective attention to negative stimuli. Following behavioral and symptom assessment participants will receive 3 training sessions conducted in the fMRI scanner, during which participants will view overlaid neutral scenes and negative faces while attending to the scenes. Multivariate pattern analysis will quantify attention to the scenes vs. faces in real-time using a cloud-based framework that adjusts each subsequent image to reward or punish based on attention to the current image. Feedback will be delivered by changing the opacity of the images of the scene target vs face distractor. We have identified a potential neural locus of the negative attentional bias — the inability of MDD to escape from a brain state in which they are attending to negative face distractors even though task irrelevant, what we refer to as “neural perseveration” (higher conditional probability of staying in the same negative state vs. healthy individuals).
- Exploratory aim: Behavioral perseveration on negative stimuli. In addition to a neural target we will also explore a behavioral perseveration target using a gaze task (R61 Exploratory Aim). In that task, patients view a screen with positive, neutral and negative images. Using an eye-tracker, the amount of time that participants spend looking at negative stimuli after first fixating on those stimuli will be recorded and compared. To further support the hypothesis that understanding negative perseveration is relevant to brain mechanisms in depression, we will measure the same probability at the end of each day of neurofeedback treatment. The progressive change over time will provide further comparisons in the active vs sham groups.
- Aim 2: Determine the lowest “dose” of training necessary to reduce selective attention to negative stimuli. Neural and behavioral markers obtained after each session will be used to determine the lowest number of sessions that produce a significant effect, which will be chosen for the R33 phase.

R33 Phase:

- Aim 1: To conduct a randomized controlled trial (RCT) to compare the effect of real-time neurofeedback vs. sham on depression outcome in patients with MDD.
- Aim 2: To determine the relationship between the markers of neural perseveration established in the R61 phase and the reduction in depressive symptoms. Neural

CONFIDENTIAL

perseveration on negative distractors and behavioral looking at negative stimuli will be correlated with MADRS scores.

- Aim 3: To determine the durability of the treatment effect.

4 Study Population and Duration of Participation

4.1 Duration of Study Participation

Following consent and ascertainment of inclusion and exclusion criteria during pre-training session, participants will be enrolled and randomized to either the active or sham group. In subsequent daily visits, they will perform the gaze task and receive neurofeedback training. In general, it is expected that the visits will occur on sequential days, except for weekends, but there will be flexibility for patient schedule. Participants will also complete a follow-up at 1 month. The patients will follow the treatment course as best as possible, however, the protocol does allow for flexibility contingent on patient availability, MRI availability, and other scheduling factors.

As a result, total duration is expected to be approximately 6 weeks, with some room for flexibility in scheduling. A schedule of visits for Phase R66 is included below:

Visit	Pre NF	NF 1	NF 2	NF 3	Post NF	1 Month
Inclusion/Exclusion	SCID-5	-	-	-	-	-
Depression Severity	MADRS	MADRS	MADRS	MADRS	MADRS	MADRS
Mood Symptom Self Report	STAI & MASQ					
MRI Acquisition	-	Structural	-	-	-	-
	-	Go/no-go	Go/no-go	Go/no-go	-	-
Behavioral Assessment	Gaze	Gaze	Gaze	Gaze	-	-

4.2 Total Number of Subjects and Sites

Enrollment and administrative site will be at the University of Pennsylvania.

R61 Phase will enroll 60 patients with MDD, and R33 Phase will enroll 80 patients with MDD. To account for attrition 60 participants will be enrolled in R61 Phase with 54 anticipated to complete full data collection (27 in each arm). To account for attrition 80 participants will be enrolled in R33 Phase with 72 anticipated to complete full data collection (36 in each arm).

4.3 Inclusion Criteria

- gender, inclusive
- adult aged 18 – 65

CONFIDENTIAL

- meets Diagnostic and Statistical Manual of Mental Disorders (DSM-5) criteria for MDD according to the Clinician-Administered MDD Scale for DSM-5 (unipolar depression or bipolar II depressed)
- scores at least a minimum score of 16 on Montgomery Asberg Depression Rating Scale (MADRS)
- normal cognition
- participants must be able to read and understand English
- participants must be able to provide consent

4.4 *Exclusion Criteria*

- pregnancy (female participants)
- outside age range
- MRI contraindications (medical implant, claustrophobia, etc.)
- use of psychoactive medication (including antidepressants) or currently in therapy
- neurological disorder or any condition that in the view of the PI could impact brain data, cause depression, require medication that could cause depressive symptoms, or otherwise result in participant being unfit for study (for example, co-morbid psychotic, neurological disorders, developmentally or cognitively disabled/impaired, active alcohol or drug abuse/dependence within the past 6 months).
- non-English speaking
- non-correctable vision loss
- refusal to provide informed consent
- representing an active suicide risk

4.5 *Subject Recruitment*

All participants will be recruited through the University of Pennsylvania and surrounding community. For both phases, recruitment will occur through the Center for Neuromodulation in Depression and Stress (CNDS) directed by the PI. All subjects will express interest by initiating contact with the research staff for a center wide phone screening or self-screening procedure. All subjects fitting inclusion criteria will be approached by study staff to continue in the study. This study will also be advertised on online sources such as Facebook. Study coordinators in the present study will use the results in REDCap as a source of recruitment, at which point those subjects will undergo the full phone-screen. This phone screen will also be collected and stored in REDCap. In addition to recruiting from the CNDS, we will recruit from the larger Philadelphia community through targeted advertisements and referral streams at the University of Philadelphia. This includes both print and online sources. All recruitment materials, including but not limited to flyers, brochures, referral letters, online postings, and email templates will be IRB-approved before distribution of any of these material.

4.6 *Vulnerable Populations:* N/A

Children, pregnant women, fetuses, neonates, or prisoners are not included in this research study.

CONFIDENTIAL

5 Study Procedures

In the R61 phase we will compare cloud based real time fMRI feedback with placebo (sham feedback) in reducing negative attention bias and depressive symptoms. This study will be the first dose-finding test of real-time fMRI effect on negative attention bias.

In the R33 phase, if approved in future, we will compare the effect of real-time neurofeedback vs. sham on depression outcome in patients with MDD. The number of training sessions will be determined in the R61 phase.

Sources of data includes fMRI data from MRI scanner, clinical evaluations (SCID, MADRS), self-report questionnaires (STAI & MASQ), and behavioral gaze data (behavioral assessment from go/no-go task). Below is a table that outlines what assessments and procedures will be completed at each visit:

Procedure	Pre-training Session (Screening Visit)	Training Session 1	Training sessions (2-3)	Post-training session	Follow-up Session
Clinical Assessments	X (SCID & MADRS)	X (MADRS)	X (MADRS)	X (MADRS)	X (MADRS)
Self-report Questionnaires	X	X	X	X	X
Medication History	X				
Demographics Survey	X				
MRI Scan		X (baseline)	X		
Behavioral Task	X	X	X		

During the initial week, there will be one initial pre-training/screening visit (approx. 3-4 hours), 3 training visits (approx. 4-5 hours each), and one post-training visit (approx. 1 hour). Within 3 months, there are 2 follow-up sessions after the treatment is over (approx. 1 hour each).

Does your study use MRI? (CAMRIS is the appropriate contact for all studies involving MRIs)

Yes No (If No, no CAMRIS review needed)

Check of all that apply:

[1.5T MRI](#)
 [3T MRI](#)
 [7T MRI](#)

Does the MRI use investigational sequences and/ or coils?

(See Experimental Device Clause)

Yes No Unsure (if unsure be sure to contact

CONFIDENTIAL

Does your study include pregnant women?

(See Pregnancy Clause and Justification)

CONFIDENTIAL

This material is the property of the University of Pennsylvania.

Yes No

Does the MRI require the use of Contrast Agents?

(See Contrast Risks)

Yes No

Does your study involve the exposure to radiation, radiotracers and/or radiological imaging modalities?

Yes No (If No, no RRSC review is needed)

Will any of the radiation exposure result from procedures that are or could be performed solely as a result of a subject's participation in the research protocol?

Yes No

The following are examples of procedures involving ionizing radiation:

(Review [appendix 15.3](#) and [appendix 15.5](#))

- X-rays (examples: CT scan, chest x-ray, hand/wrist x-ray, abdomen x-ray, DEXA, pQCT, Fluoroscopy/Angiography)
- Nuclear Medicine scans (examples: FDG-PET, PET/CT, Tc-99m, SPECT, MUGA, bone scan)
- If you are unsure please contact [name] in EHRS ([contact]).

Ultrasound

Yes No

If yes, there is no protocol specific language to include but please contact [name] at: [contact]

Will your study be using CT Scans? (CACTIS is the appropriate contact for studies involving CT scans)

Yes No

Studies involving Nuclear Medicine: Will subjects be undergoing any of the following procedures specific to research:

MUGA

(See Nuclear Medicine-Muga Scan)

PET/CT Scan

(See PET/CT Scan)

Bone /DXA

(See Bone Scan)

Check off all of the following procedures that will be performed in your research- each option you select will link to the template language document:

Apheresis/plasma exchange

CONFIDENTIAL

- [Leukapheresis](#)
- [Bone Marrow Biopsy or Aspirate](#)
- [Use of AP clinical specimens](#)
- [Biopsies- check those which apply](#)
- [Blood draw](#)

5.1 *Pre-Training Visit*

The pre-training visit will include screening procedures.

Participants will be recruited, consented, and evaluated. They will also complete MRI safety screening forms and self-report medical history. This includes completing informed consent. Each patient's medical history is reviewed by [name] and, when clinically indicated, a physical examination and appropriate laboratory tests will be obtained to ensure that patients are diagnostically eligible. Consenting patients will be diagnosed with the Structured Clinical Interview for DSM-5. Participants who meet eligibility requirements will be screened using the MADRS, which will be the primary outcome measure and will have a minimum score of 16. Participants will also complete the STAI & MASQ.

In addition to a neural target we will also explore a behavioral perseveration target using a gaze task. In that task, patients view a screen with positive, neutral and negative images. Using an eye-tracker, the amount of time that participants spend looking at negative stimuli after first fixating on those stimuli will be recorded and compared. To further support the hypothesis that understanding negative perseveration is relevant to brain mechanisms in depression, we will measure the same probability at the end of each day of neurofeedback treatment. The progressive change over time will provide further comparisons in the active vs sham groups.

5.2 *Study Intervention or Observational Phase (Give this section a name that is relevant to the design of your study)*

5.2.1 *Training Visit 1*

Following ascertainment of inclusion and exclusion criteria and consent, participants will be enrolled and randomized to either the active or sham group. The active training group will receive baseline structural and functional MRI scans, which will function as the baseline MRI scans. Participants will also perform the behavioral gaze task and complete a MADRS, STAI, and MASQ.

5.2.2 *Training Visits 2-3*

In subsequent daily visits, they will perform the gaze task and receive neurofeedback training. Participants will also complete a MADRS, STAI, and MASQ.

CONFIDENTIAL

5.2.3 Post-training Visit

During the post-neurofeedback training session, participants will complete only a MADRS, STAI, and MASQ.

5.2.4 Follow-up Visits 1-2

Participants will also complete 1 follow-up visit: at one month from the post treatment visit, participants will complete MADRS, STAI, and MASQ during these follow-up visits.

5.2.5 End of Study Visit

N/A

5.3 *Unscheduled Visits*

Unscheduled visits will be handled only if deemed necessary by study staff, for instance a participant presented to the ER during study participation, study staff may request the patient come in between visits for evaluation.

5.4 *Subject Withdrawal*

Participants may be withdrawn from the study by staff if deemed necessary for their health or safety or if participants have not been following instructions. We anticipate that some participants may withdraw. We do not expect early termination of participation due to patient or investigator withdrawal to have any impact on safety or well-being of participants.

5.4.1 Data Collection and Follow-up for Withdrawn Subjects

N/A

5.5 *Early Termination Visits*

If deemed necessary to terminate a patient's participation in the study, they will be contacted by study staff to communicate this and the reason why. No other information will be collected from the terminated participant. Participant will complete end-of-study procedures as needed (receiving compensation, etc.).

5.6 *Efficacy Evaluations (only if applicable)*

Montgomery Asberg Depression Rating Scale (MADRS) will be used to examine efficacy of study intervention.

CONFIDENTIAL

5.7 ***Pharmacokinetic Evaluation (only if applicable):*** N/A

5.8 ***Genetic Testing (only if applicable):*** N/A

5.9 ***Safety Evaluation (only if applicable)***

The primary investigator will routinely monitor and evaluate study procedures for potential increased risk.

6 Statistical Plan

6.1 ***Sample Size and Power Determination***

R61 Phase: A total of 60 (n=30 active neurofeedback, n=30 sham feedback) will be enrolled. Allowing for a 10% loss of subjects, based on our preliminary data, the sample size (i.e. at least 27 patients per arm with valid post-treatment data) was chosen so that the study would have adequate power to detect between-group differences of moderate to large between group effect sizes (see power analysis below).

- For a one-sample t-test with a two-sided alternative and type I error rate of 5%, 27 participants will yield 80% power for a Cohen's $d = 0.56$. This is sufficient power to detect the effect size of $d = 0.83$ for reduction in neural perseveration found in the pilot study. For a two-sample t-test with two-sided alternative and type I error rate of 5%, 27 participants per arm will yield 80% power for a Cohen's $d = 0.86$ or larger. The statistical analysis for power determination and sample size is subject to change as data is collected over the course of the study.

R33 Phase: A total of 80 participants with MDD (n=40 real time neurofeedback, n=40 sham feedback) will be enrolled as above in a randomized controlled clinical trial. Allowing for a 10% loss of subjects, based on our preliminary data, the sample size (i.e. at least 36 patients per arm with valid post-treatment data) was chosen so that the study would have adequate power to detect between-group differences of moderate to large between group effect sizes (see power analysis below).

- For a one-sample t-test with a two-sided alternative and type I error rate of 5%, 36 participants per arm will yield 80% power for a Cohens $d = 0.53$ or larger, which is sufficient to detect the effect size of 0.93 Visit 1 to post-treatment MADRS score decrease in the pilot data (**Hypothesis 1**). For a two-sample t-test with a two-sided alternative and type I error rate of 5%, 36 participants will yield 80% power for a Cohens $d = 0.74$ or larger. **Hypothesis 2** will utilize Pearson correlation between change in MADRS and change in negative attention scores. If nonlinearity is detected, we will employ a Spearman correlation analysis. A sample size of n=36 corresponds to 80% power to detect a significant (at 5% alpha level) correlation as low as $r=0.45$, which is sufficient to detect the effect size of $r=0.48$ found in the pilot data (**Figure 1**). **Hypothesis 3** will use a two-sample t-test comparing real vs sham NF. Pilot study data indicated a change in MADRS from baseline to 3 month follow-up corresponding to Cohen's $d=0.95$. A two-sample t-test, with 36 per group, at 5% significance level, gives 80% power to detect $d=0.74$ or larger.

CONFIDENTIAL

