7.1.2 Serious Adverse Event

Serious Adverse Event

CONFIDENTIAL

Adverse events are classified as serious or non-serious. A serious adverse event is any AE that is:

- fatal
- life-threatening
- requires or prolongs hospital stay
- results in persistent or significant disability or incapacity
- required intervention to prevent permanent impairment or damage
- a congenital anomaly or birth defect
- an important medical event

Important medical events are those that may not be immediately life threatening, but are clearly of major clinical significance. They may jeopardize the subject and may require intervention to prevent one of the other serious outcomes noted above. For example, drug overdose or abuse, a seizure that did not result in in-patient hospitalization, or intensive treatment of bronchospasm in an emergency department would typically be considered serious.

All adverse events that do not meet any of the criteria for serious should be regarded as non-serious adverse events.

For additional information on definitions and clarifications which may be helpful in creating the safety monitoring portion refer to [appendix 15.7](#)

7.2 *Recording of Adverse Events*

At each contact with the subject, the investigator will seek information on adverse events by specific questioning and, as appropriate, by examination. Information on all adverse events will be recorded immediately in the source document, and also in the appropriate adverse event module of the case report form (CRF). All clearly related signs, symptoms, and abnormal diagnostic procedures results should be recorded in the source document, though should be grouped under one diagnosis.

All adverse events occurring during the study period will be recorded. The clinical course of each event will be followed until resolution, stabilization, or until it has been determined that the study intervention or participation is not the cause. Serious adverse events that are still ongoing at the end of the study period will be followed up to determine the final outcome. Any serious adverse event that occurs after the study period and is considered to be possibly related to the study intervention or study participation will be recorded and reported immediately.

7.3 *Relationship of AE to Study*

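### Section 5.5 bars collecting further information from a staff-terminated participant with no safety exception, which contradicts the adverse-event questioning that 7.2 requires at each contact

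*Combined protocol and SAP*

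**What the plan says.** Section 5.4 (Subject Withdrawal) gives staff the power to remove people: "Participants may be withdrawn from the study by staff if deemed necessary for their health or safety". It also allows removal for not following instructions.

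Section 5.5 (Early Termination Visits) sets out what then happens. Participants are told: "they will be contacted by study staff to communicate this and the reason why". The next sentence is the rule at issue: "No other information will be collected from the terminated participant". After that, only end-of-study procedures remain, as needed, with compensation as the one named example. Section 5.4.1, the heading intended for data collection and follow-up after withdrawal, is marked N/A.

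Section 7.2 (Recording of Adverse Events) sets the safety rules:

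- On questioning: "At each contact with the subject, the investigator will seek information on adverse events by specific questioning".
- On open events: "The clinical course of each event will be followed until resolution, stabilization, or until it has been determined" that the study is not the cause.
- On serious events: "Serious adverse events that are still ongoing at the end of the study period will be followed up to determine the final outcome".

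Section 7.4.1 adds follow-up reports to the IRB on an unresolved serious event until it resolves or stabilizes. None of these provisions exempts terminated participants, and 5.5 does not mention section 7.

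**The concern.** Two unqualified instructions apply to the same contact. A coordinator phoning a participant to end their involvement is told by 7.2 to ask about adverse events and by 5.5 to collect nothing more. No provision says which rule prevails.

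The people involved include those removed for health or safety, who may well have an event in progress. If 5.5 is followed to the letter, new events are not asked about at the last planned conversation, and the later course of an open event is not obtained from the person who has it. Other informants are permitted, but they may be scarce: section 4.4 excludes anyone in therapy or on psychoactive medication at entry, so a treating mental-health clinician cannot be assumed.

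**Working it through.** No arithmetic applies, and the plan states no figure to reproduce. The check is to set the provisions side by side and ask what 5.5, read as written, forbids.

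**1. Questioning at the termination contact.** Section 5.5 requires staff to contact the participant, and 7.2 is triggered by each contact. Section 7.2 names the investigator as the one who asks, while 5.5 speaks of study staff. That does not separate the two rules, because the trigger in 7.2 is the contact, and 9.1 has the clinical assessment team gather adverse-event information. Asking the 7.2 questions means collecting information from the participant, which 5.5 forbids. This is a direct contradiction.

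**2. End-of-study procedures.** These might create a further contact, to which the same reasoning would apply. The documents do not show that they do. The only example is compensation, which section 11.3 pays by card, and 5.2.5 (End of Study Visit) is marked N/A. Nothing should rest on this.

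**3. Following open events.** Section 7.2 requires the course of each event, and the outcome of ongoing serious events, to be followed, but it does not say from whom. Section 5.5 closes one route, the participant. Treating clinicians and records stay open. Follow-up is therefore narrowed, not prohibited.

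**4. Recording and reporting.** Section 7.2 also covers later events: "Any serious adverse event that occurs after the study period and is considered to be possibly related to the study intervention" or participation is to be recorded and reported immediately. Like the IRB follow-up reports in 7.4.1, this is a duty of the study team. Section 5.5 limits collection from the participant and does not restrict either duty. Events already known still go to the IRB under 7.4. Dropouts, their reasons and adverse events still go to the DSMB under 7.4.3.

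**5. Is there text that settles the conflict?**

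| Place | What it offers | Does it qualify 5.5? |
|---|---|---|
| 5.4 | Expects no effect of early termination on safety or well-being | No; it is an expectation, not a collection rule |
| 5.4.1 | N/A | No |
| 5.3 | Unscheduled visits, illustrated by an event while the person is still participating | No |
| 9.1 | Adverse events gathered at clinical visits and escalated | No; silent on what happens after termination |
| Appendix 15.6, Post-study Adverse Event | Unresolved events should be followed until resolved, lost to follow-up or otherwise explained; reasonably related events after discontinuation or termination should be notified to the sponsor | No; it shows likely intent, but does not mention 5.5 |

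The appendix comes closest. Staff termination is not among its reasons to stop following an event, and section 7.1.2 sends readers to the safety appendix for clarification. But it is general reference text worded as advice, and 7.4.2 marks sponsor notification as N/A. It points towards continued follow-up without lifting the bar in 5.5.

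**The case against.** The best answer is that 5.5 should be read in its place. It sits among the study procedures, under a heading about early termination visits, in a section whose stated data are scans, clinical ratings, questionnaires and gaze. On that reading it waives a final assessment battery and leaves safety to section 7, which is mandatory in tone. The appendix supports this. An event that prompts removal for safety would also normally be known already, since 9.1 has adverse events gathered at clinical visits and escalated, and 10.3 describes the study as minimal risk.

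Much of this stands. It is probably what the authors intended, and it keeps the practical consequence small. It does not remove the contradiction: the sentence excludes all other information, not merely further assessments, and the people applying it should not have to infer an exception. If the narrow reading is right, the proposed clause simply states it.

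A reader might infer more than the documents support:

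- **That 5.5 abolishes all safety follow-up and reporting after termination.** It restricts only what is collected from the participant.
- **That anyone who leaves goes unfollowed.** Section 5.5 concerns termination by the study, not participants who leave of their own accord.
- **That the consent form is deficient.** The form is not in the text reviewed, and it may already cover safety contact after termination.

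**Conclusion.** The contradiction is real and narrow. Section 5.5 conflicts directly with 7.2 on adverse-event questioning at the termination contact. Read literally, it also takes away the participant as a source for following open events. Other sources, recording, and IRB and DSMB reporting are unaffected.

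The size cannot be put as a number. The documents give neither the frequency of staff terminations nor the share of those participants with an open event, so no count or bound is offered.

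The conclusion assumes that the words of 5.5 mean what they say and that the termination contact counts as a contact under 7.2. This is a minor safety correction worth making because it is cheap and covers people removed for health or safety.

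**What to change.** - **Section 5.5:** keep the sentence "No other information will be collected from the terminated participant" and add to it: *except adverse-event information and follow-up of open events under 7.2 and 7.4.1, where the participant agrees.*
- **Termination contact:** ask the 7.2 adverse-event questions and record the status of every open event.
- **Section 5.4.1:** replace N/A with a cross-reference to this rule for staff-terminated participants.
- **Consent form:** check that it is consistent with the rule; do not assume that it needs changing.

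The cost is one clause, one cross-reference and a few extra questions or contacts, which 7.2 already implies. Some participants may decline, which is why the exception depends on their agreement. No endpoint, sample size or analysis changes.

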6.2 Statistical Methods

Statistical analysis will be performed using the R statistical environment assuming 5% type I error rates. Linear mixed effects regression modeling (using the lme4 R package) will be used to assess evidence of reduced neural perseveration and reduced MADRS over time in the active neurofeedback group. Two-sample t-tests will be used to compare differences in neural perseveration and MADRS scores between the active neurofeedback and sham (yoked) neurofeedback groups after each additional session of treatment in order to establish the lowest dose of training necessary to significantly reduce neural perseveration. We will utilize multiple linear regression to assess the relationship between reduced perseveration and the reduction of MADRS scores in the active neurofeedback group while accounting for various confounds.

6.3 Control of Bias and Confounding (if applicable, typically observational study or if randomization is not taking place)

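### Section 6.1 prints detectable effects of 0.86, 0.53 and 0.74 (twice) for 80% power; its stated sample sizes at two-sided 5% give 0.78, 0.48 and 0.67

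*Combined protocol and SAP*

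**What the plan says.** Section 6.1 gives six detectable effects at 80% power, after allowing 10% loss (30 to 27 per arm in R61, 40 to 36 per arm in R33).

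- R61, one-sample: "27 participants will yield 80% power for a Cohen's $d = 0.56".
- R61, two-sample: the sentence opens "For a two-sample t-test with two-sided alternative and type I error rate of 5"% and continues "27 participants per arm will yield 80% power for a Cohen's $d = 0.86$ or larger".
- R33 Hypothesis 1, one-sample, two-sided 5%: "36 participants per arm will yield 80% power for a Cohens $d = 0.53$ or larger".
- R33, two-sample, two-sided 5%: "36 participants will yield 80% power for a Cohens $d = 0.74$ or larger".
- R33 Hypothesis 2, correlation: "A sample size of n=36 corresponds to 80% power to detect a significant (at 5% alpha level) correlation as low as $r=0.45".
- R33 Hypothesis 3, two-sample, 36 per group at the 5% level: "gives 80% power to detect $d=0.74$ or larger".

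Section 6.2 sets the level for the analyses, "assuming 5% type I error rates". Neither section mentions a divided or adjusted alpha.

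**The concern.** A detectable effect is fixed once the test, n, alpha and power are given, and 6.1 gives all four. Four of its six figures do not follow from them. Three of those four are the between-group values. Section 6.1 justifies both sample sizes by power for between-group differences, and section 6.3.2 names the two-sample t-test on MADRS as the analysis of the primary outcome.

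The trial is not too small on this account. What is at stake is whether the power statement can be reproduced, and whether the stated 5% is the level actually used. If part of the power analysis was run at a stricter level, the plan should say so. One sufficiency claim, the one for the correlation, would be sensitive to that.

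**Working it through.** **Inputs (section 6.1).** Two-sided alpha 0.05; power 0.80; n = 27 (R61) and n = 36 (R33), as a single group for the one-sample test and per arm for the two-sample test. Two readings are needed. The first R33 two-sample sentence gives 36 without a unit and is read as per arm, as the Hypothesis 3 sentence states. Hypothesis 3 does not restate that its test is two-sided and is read as such.

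**Formula.** Power = P(|T| > t*), where T is noncentral t and t* is the 1 − alpha/2 quantile of central t.

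- One-sample: df = n − 1, noncentrality = d√n.
- Two-sample: df = 2n − 2, noncentrality = d√(n/2).

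Set power to 0.80 and solve for d.

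**Reproducing the figures that are right.**

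- One-sample, n = 27: df = 26, t* = 2.056, required noncentrality 2.911, so d = 2.911/√27 = 0.560. Printed 0.56.
- Correlation, n = 36, Fisher z: r = tanh[(1.960 + 0.842)/√33] = 0.452. Printed 0.45.

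So the stated method and level are the right benchmark.

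**The figures that do not reproduce.**

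- Two-sample, 27 per arm: df = 52, t* = 2.007, required noncentrality 2.855, so d = 2.855/√13.5 = 0.777.
- One-sample, n = 36: df = 35, t* = 2.030, required noncentrality 2.881, so d = 2.881/6 = 0.480.
- Two-sample, 36 per arm: df = 70, t* = 1.994, required noncentrality 2.841, so d = 2.841/√18 = 0.670.

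| Test | Printed d | d at 5% | Ratio | Power at printed d, 5% | Smallest n for 80% at printed d, 5% |
|---|---|---|---|---|---|
| Two-sample, 27/arm | 0.86 | 0.777 | 1.11 | 87.3% | 23/arm |
| One-sample, n = 36 | 0.53 | 0.480 | 1.10 | 87.1% | 30 |
| Two-sample, 36/arm (printed twice) | 0.74 | 0.670 | 1.10 | 87.2% | 30/arm |

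**Other readings tried** (in the order of the table).

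- Normal approximation: 0.76, 0.47, 0.66. No match.
- One-sided 5%: 0.69, 0.42, 0.59. Further away.
- Enrolled n (30 and 40): 0.74, 0.45, 0.63. No match.
- 36 as a total (18 per arm): 0.96. No match for 0.74.
- n = 30 at 5%: 0.53 one-sample and 0.74 two-sample. This would explain the R33 values but not 0.86 in R61.
- Two-sided 2.5% at the stated n: 0.860, 0.533, 0.740. All match.
- 87% power at two-sided 5%: 0.856, 0.529, 0.738. Also matches to two decimals, but it contradicts the stated 80% and is not a conventional target.

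**Effect on the sufficiency statements.** At 5%, power for the pilot effects is 98.6% (one-sample d = 0.83, n = 27), over 99.9% (one-sample d = 0.93, n = 36) and 85–86% (r = 0.48, n = 36; the range covers Fisher z and a t-based critical value). If 2.5% applied throughout, the R61 one-sample value would be 0.62, still below 0.83. The detectable correlation would be tanh[(2.241 + 0.842)/√33] = 0.490 (0.487 by the t-based method), just above the pilot 0.48, with power of 78–79% at 0.48.

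**The case against.** The best defence is that nothing follows from the error. At the declared 5% the printed values overstate the detectable effect, so the trial has more power than claimed. No sample size, test or conclusion changes. Each disputed sentence also covers larger effects, so read literally as at least 80% power from that size upward, each is true, only not sharp. That stands as far as it goes, and it is why the point is not graver. It does not clear the text, because such a sentence is ordinarily read as the minimum detectable effect, and the two correct figures in the section are minimum values.

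A second objection is that alpha is not in doubt, since 6.1 and 6.2 both state 5%, and 2.5% is only a back-calculation. This is fair: 2.5% is an inference, and other settings can be made to fit. Even if a stricter level was meant for some tests, it need not extend to the correlation or the R61 one-sample test. The consequence for r = 0.48 is therefore conditional. The corrected values at 5% do not depend on how the error arose.

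**Conclusion.** The concern holds. At the stated n, two-sided 5% and 80% power, the detectable effects are 0.78, 0.48 and 0.67 where section 6.1 prints 0.86, 0.53 and 0.74 (twice). The discrepancy is about 10% in effect size, or about 7 percentage points of power. It is conservative and leaves the sample sizes intact. It should still be fixed, because every between-group figure given in support of those sample sizes is wrong for its own inputs, and the section mixes values that fit 5% with values that do not.

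This rests on reading the unlabelled 36 as per arm and Hypothesis 3 as two-sided; neither alternative reading yields 0.74. The cause is not established. A two-sided 2.5% level is the only conventional setting tried that reproduces all the wrong values.

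**What to change.** Confirm which alpha was entered in each calculation, then make the text agree with it.

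- If 5% stands, as 6.1 and 6.2 say: in 6.1 replace 0.86 with 0.78, 0.53 with 0.48, and both instances of 0.74 with 0.67. State that 36 is per arm in the R33 two-sample sentence, and that the Hypothesis 3 test is two-sided.
- If 2.5% per test was intended: declare it in 6.1 and 6.2, with the reason and the tests it covers. If it covers all of them, restate the R61 one-sample value as 0.62 and the detectable correlation as about 0.49, and reword the claim that n = 36 suffices for the pilot r = 0.48.

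The cost is a text correction. Sample sizes, tests and trial conduct do not change.
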